## 15.2 Informed Consent Process

### 15.2.1 Informed Consent Procedure and Documentation

Subjects informed consent must be obtained and documented according to the principles of informed consent in the latest version of the Declaration of Helsinki (Brazil, 2013), ISO 14155:2011, and approved by the reviewing Regulatory Authority and EC

Informed consent is mandatory and must be obtained from all subjects prior to their participation in the study.

Prior to screening or performing any study related procedures that are solely for the purpose of determining eligibility for this study, any potential benefits and risks of the study must be explained to the subject. Subjects will be informed about aspects of the study that are relevant to the subject's decision to participate. Subjects should be made aware that by signing the Informed Consent Form (ICF), they are granting approval for study personnel to review their medical records and to collect/analyze personal medical information. Subjects should also be informed that study personnel will maintain confidentiality of the medical records at all times.

The ICF will be written in a native, non-technical, language that is understandable to the subject and is to be approved by the applicable EC prior to enrolling subjects. The subject or designee will be provided with ample time to read and understand the ICF and to consider participation in the study. Informed consent will be requested prior to enrollment and must

be personally signed and dated by the subject, or subject's legal representative, prior to performance of any study related activity or procedure. If a subject is unable to read or write, informed consent shall be obtained through the aid of an independent witness who will be present throughout the process. The written ICF and any other information shall be read aloud and explained to the prospective subject and, whenever possible, subject shall sign and date the ICF. The witness must also sign and date the ICF attesting that the information was accurately explained and that informed consent was freely given. The point of enrollment corresponds with the time that subjects signs the informed consent.

The investigator and/or designee must also clearly document the process of obtaining informed consent in the subject's source documents. The voluntary process of obtaining informed consent confirms the subject's willingness to participate in the study. It's the investigator's responsibility to ensure that the informed consent process is performed in accordance with ICH-GCP and, where applicable, local and federal regulations. Subjects should not be coerced, persuaded, or unduly influenced to participate or continue to participate in the trial. Subjects or his/her legal representative must be given ample time and opportunity to inquire about details of the trial and all questions about the trial should be answered to the satisfaction of the patient or the representative. Failure to provide written informed consent renders the subject ineligible for the study. If new information becomes available that can significantly affect a subject's future health and/or medical care, this information shall be provided to the subject(s) affected in written form. If relevant, all affected subjects shall be asked to confirm their continuing informed consent in writing by dating and signing the amended ICF.

### **15.3 Participant and Data Confidentiality**

During this clinical investigation, all representatives of the Sponsor will comply with all in-country privacy laws and regulations regarding contact with subjects, their medical record information, copying of information, and protection of the subject identities.

All information and data sent to Biosense Webster concerning subjects or their participation in this clinical investigation will be considered confidential. Only authorized Biosense Webster personnel or representatives (including contracted service providers, i.e. Core Lab, Clinical Research Associate, CRO, etc.), representatives of the FDA or Competent Authorities acting in their official capacities will have access to these confidential files upon request (including, but not limited to, laboratory test result reports, ECG reports, admissions/discharge summaries for hospital admission occurring during a patient's study participation and autopsy reports for deaths occurring during the clinical investigation). Some of the countries to which the study subjects and investigators personal data may be transferred may not offer as comprehensive a level of protection of personal data as within the European Union but Sponsor will take all reasonable steps to ensure a sufficient level of data protection. All data used in the analysis and reporting of this evaluation will exclude identifiable reference to the subject.

### 15.3.1 Research use of Stored Data

- Intended Use: Data collected under this protocol may be used to study Atrial Fibrillation.
- Storage: Access to stored data will be limited. Data will be stored using codes assigned by the sponsor. Data will be kept in password-protected computers. Only investigators and the sponsor will have access to the data.

## 16 Source Documents and Access to Source Data/Documents

Data entered on to the eCRFs will be taken from source documentation, such as hospital procedure reports, admission and discharge summaries, other hospital or investigator office/clinic documents, and system data (CARTO, generator). If unique study parameters are not documented on standard hospital or office reports, a worksheet may be developed to record this information. The worksheet shall be signed by the PI or authorized designee and will serve as source document and as basis for monitoring the eCRFs. Electronic subject records will be considered as source documents on the condition that the hospital's database is a validated system. If this is not the case, electronic records should be printed and added to the subject's paper file. A print-out of a completed eCRF cannot be used as source documentation.

Investigators should maintain information in the subject's medical records, which corroborate data collected on the eCRFs. In order to comply with these regulatory requirements, at minimum, the following is a list of information that should be maintained.

- Medical history/physical condition of the study subject before involvement in the study sufficient to verify protocol selection criteria (if not already present).
- Dated and signed notes from the day of entry into the study including the study Sponsor (Biosense Webster), protocol number, clinical site, subject number assigned and a statement that consent to participate in the study was obtained.
- Dated and signed notes from each study visit with reference to the eCRFs for further information, if appropriate (for specific results of procedures and exams).
- Reports on AEs and their resolution, including supporting documents such as discharge summaries, EP lab reports, ECGs, lab results.
- Notes regarding protocol-required medication and prescription medications taken during the study (including start and stop dates).
- Notes on subject's condition upon completion of or withdrawal from the study.

Only authorized Biosense Webster personnel or representatives, authorized site personnel, local government authorities, or the FDA, acting in their official capacities, will have access to these confidential files.

## 17 Quality Assurance and Quality Control

QC procedures will be implemented beginning with the data entry system and ongoing QC checks will be run on the database. Any missing data or data anomalies will be communicated to the site(s) for clarification/resolution.

Following written SOPs, monitors will verify that the clinical trial is conducted and data are generated, documented, and reported in compliance with the protocol, GCP, and the applicable regulatory requirements. If noncompliance is identified, Sponsor is required by regulation to implement measures to secure compliance.

The investigational site will provide direct access to all trial related sites, source data/documents, and reports for the purpose of monitoring and auditing by the sponsor, and inspection by local and regulatory authorities.

## 18 Data Handling and Record Keeping

### 18.1 Data Collection and Management Responsibility

The Sponsor will be responsible for all data management activities. These activities include development of an electronic data collection (EDC) system and utilizing a validated EDC system into which all study data will be entered. The Sponsor will be responsible for reviewing all data to ensure the overall integrity of the database.

#### 18.1.1 Data Collection

Electronic Case Report Forms (eCRFs) will be used to collect all subject data during this clinical investigation. eCRFs have been developed to capture the information outlined in this clinical investigation Plan. Modification to the eCRF will only be made if deemed necessary by the sponsor. Data on these eCRFs will be monitored (source verified) and the monitor will ask the site representative to correct if necessary to match the source documents. All changes made to the data will be tracked in the electronic audit trail. The investigator will be required to sign designated eCRFs as verification that they have been reviewed and the data entered are correct. Data from these eCRFs will be used to provide analysis of this clinical investigation.

#### 18.1.2 Data Reporting

The investigator, or a designated individual, is responsible for ensuring that clinical investigation data are timely and properly recorded on each subject's eCRF and related documents. The investigator, or a designated individual, is required to electronically sign the eCRF on the appropriate pages to verify that he/she has reviewed and attests to the correctness of the recorded data. Completed eCRF will be reviewed and monitored by the sponsor personnel, or an appropriately qualified and trained designee, throughout the clinical investigation. To this end, the Investigator and institution must permit inspection of the trial files and subject eCRFs by such representatives and/or responsible government agencies.

Investigators are required to prepare and submit accurate and timely reports on this study to the governing EC and Biosense Webster.

**Table 18.1.2-A: Responsibilities for Preparing and Submitting Reports**

Type of Report	Prepared by Investigator For	Time of Notification
Subject withdrawal	Biosense Webster	Should report within 5 working days
Withdrawal of EC approval	Biosense Webster	Should report within 5 working days
Final report	Biosense Webster, EC	Will prepare a final report for the clinical investigation as required per national regulations.
Informed consent not obtained from subject	Biosense Webster, EC	Should report within 5 working days

It is recommended that all eCRF data be entered by the designated site personnel as soon as possible. For AE reporting, refer to the Adverse Event Reporting Requirements and timelines noted within this clinical investigation protocol.

#### 18.1.3 Data Verification and Review

Biosense Webster will track the amount of missing data and contact sites as appropriate to instruct them on steps to minimize missing data and remain compliant with protocol required assessments. Missing or unclear data will be queried as necessary throughout the trial. Biosense Webster will request further documentation such as physician and/or cardiac EP lab procedure notes when complications or device malfunctions/complaints are observed and reported. Biosense Webster will be responsible for auditing the database and confirming the overall integrity of the data.

#### 18.1.4 Final Data Analysis

All exported datasets for analyses will undergo a final data review before final database lock. Once all critical data are monitored and locked, the final analyses of clinical investigation data will be performed.

## 18.2 Study Record Retention and Archiving

Records and reports for the study will remain on file at the site for a minimum of 5 years or per country specific record retention requirements following notification by the sponsor that all investigations have been terminated or completed. This documentation must be accessible upon request by the regulatory authorities, the sponsor, or a designee. The sponsor must approve archiving, transfer, and destruction of the documentation, in writing, prior to the actual archiving, transfer, and destruction. The investigator must notify the sponsor, in

writing, of transfer location, duration, and the procedure for accessing the study documentation.

If the investigator retires, relocates, or withdraws from assuming primary responsibility for keeping the study records, custody transfer per written notice must be submitted to the sponsor indicating the name and address of the person accepting primary responsibility. The EC must be notified in writing of the name and address of the new custodian. Record retention dates must be provided to all parties by the sponsor's corporation.

## 19 Study Suspension or Termination

This study may be temporarily suspended or prematurely terminated at the discretion of the Sponsor. The Sponsor may also terminate a site prior to study completion if the Sponsor believes the site is no longer capable of participating (e.g., cannot fulfill subject enrollment or protocol compliance goals, site suspension by EC). If the study is prematurely terminated or suspended, the PI will promptly inform the EC and will provide the reason(s) for the termination or suspension.

If suspension or premature termination occurs, the terminating party shall justify its decision in writing and promptly inform the other parties with whom they are in direct communication. The principal investigator and sponsor shall keep each other informed of any communication received from either the EC or the regulatory authority.

If early termination of the study is required due to safety concerns, each site will undergo a monitoring visit to conclude any outstanding issues, collect all outstanding CRF information, verify device accountability, and discuss any other items relevant to the conclusion of the study. Any enrolled subjects will continue to be followed per the study protocol requirements.

If, for any reason, the sponsor suspends or prematurely terminates the study at an individual study site, the sponsor shall inform the responsible regulatory authority as appropriate and ensure that the EC is notified, either by the principal investigator or by the sponsor. If the suspension or premature termination was in the interest of safety, the sponsor shall inform all other principal investigators.

Circumstances that may warrant termination or suspension include, but are not limited to:

- Determination of unexpected, significant, or unacceptable risk to participants
- Demonstration of efficacy that would warrant stopping
- Insufficient compliance to protocol requirements
- Data that are not sufficiently complete and/or evaluable
- Determination of futility

Study may resume once concerns about safety, protocol compliance, data quality is addressed and satisfy the sponsor, EC and regulatory agency.

## 20 Data and Publication Policy

Publications and/or presentation of clinical investigation results will be coordinated between Biosense Webster, Inc. and the clinical investigation author(s). Authorship will be determined prior to development of any manuscript. All information concerning the study, investigational medical device, sponsor operations, patent application, manufacturing processes, and basic scientific data supplied by the sponsor to the investigator and not previously published, are considered confidential and remain the sole property of the sponsor.

## 21 Document Filing

A copy of all approved versions of the Investigation Protocol will be kept, by the site, in the Investigator Site File and in the Sponsor Trial Master File.

AT	atrial tachycardia
DMC	Data Monitoring Committee
mITT	Modified Intent-To-Treat
MoCA	Montreal Cognitive Assessment
NAE	neurological assessment evaluable subgroup
NIHSS	National Institutes of Health Stroke Scale
PAE	primary adverse event
PAF	paroxysmal atrial fibrillation
PP	per-protocol
PV	pulmonary vein
PVI	pulmonary vein isolation
RF	radiofrequency
SADE	Serious Adverse Device Effects
SAE	serious adverse event

1 STUDY DESIGN

This clinical investigation is a prospective, multicenter, single arm clinical evaluation utilizing the Biosense Webster Multi-Electrode Radiofrequency Balloon catheter and the Biosense Webster Multi-Electrode Circular Diagnostic catheter.

An adaptive Bayesian design [1] will be used to determine the sample size. A maximum of 230 evaluable subjects with symptomatic paroxysmal atrial fibrillation (PAF) may be enrolled in the main study phase. Subjects enrolled in the main study phase will be evaluated at 7 days, 1, 3, 6 and 12 months following the index procedures.

To minimize the learning curve effect on the evaluation of safety and effectiveness of the multi-electrode RF balloon catheter, the first 1 to 3 roll-in subjects will be assigned to each ablating physician in this study. Based on a maximum number of 20 sites, and assuming an average of 2 ablating physicians per site, up to an estimated 60 roll-in subjects will be included in the study.

A focused neuropathological evaluation will be integrated within the Main Study. A subset of subjects enrolled in the main study phase (40 subjects) will be included in the Neurological Assessment Evaluable (NAE) subgroup. Enrollment of NAE subjects may be terminated prior to achieving the target 40 subjects if study enrollment ends early after a planned interim look. NAE subjects will be assessed for incidences of symptomatic and asymptomatic pre-and post-ablation cerebral emboli with either an absence of CNS deficits (asymptomatic) or with emboli-associated neurological symptoms (symptomatic).

2 TREATMENT ASSIGNMENT

This is a single-arm study. The only treatment assigned is the Multi-Electrode Radiofrequency Balloon catheter.

3 RANDOMIZATION AND BLINDING PROCEDURES

This study is a non-randomized single-arm study. Therefore, masking of treatment assignment for operators and subjects will not be performed.

4 MEASURES TO MINIMIZE BIAS

This study will employ several measures to minimize operational bias.

- Timing of the interim analyses for sample size selection will not be revealed to sites
- An independent statistician will be responsible for performing interim analyses
- Results from the interim analyses will not be shared with the Sponsor or sites unless the interim analysis results in a decision to stop enrollment

Biosense Webster, Inc

- Sponsor personnel directly involved in the conduct of the study will not have access to intermediate aggregated summaries of primary or secondary safety and effectiveness endpoint data until decision of study enrollment adaptation has been made

5 INTERVAL WINDOWS

Refer to protocol Table 8.7A.

6 STUDY ENDPOINTS

6.1 Primary Endpoints and Associated Hypotheses

6.1.1 Primary Safety Endpoints

The primary safety endpoint is the incidence of early onset Primary Adverse Events (PAEs) (within seven (7) days of the initial mapping and ablation procedure). PAEs include the following AEs.

Death*	Stroke/CVA
Atrio-Esophageal Fistula*	TIA
Myocardial Infarction	Phrenic Nerve Paralysis
Cardiac Tamponade/perforation	Pulmonary Vein Stenosis*
Thromboembolism	Major Vascular Access Complication/Bleeding

* Device or procedure related death, pulmonary vein stenosis and atrio-esophageal fistula that occur greater than one week (7 days) and less than or equal to 90 days post procedure are considered and analyzed as primary AEs.

The PAE rate will be compared against the performance goal of 15% by testing the following hypotheses:

$$H_0: p_S \geq 0.15 \quad \text{vs.} \quad H_A: p_S < 0.15,$$

where p_S is the PAE rate.

6.1.2 Primary Effectiveness Endpoints

The primary effectiveness endpoint of this study is the proportion of subjects with acute procedural success defined as confirmation of entrance block in treated pulmonary veins (PV) after adenosine and/or isoproterenol challenge (with or without the use of a focal catheter). The hypotheses to be tested for this evaluation are:

$$H_0: p_E \leq 0.80 \quad \text{vs.} \quad H_A: p_E > 0.80,$$

where p_E is the rate of acute procedural success.

6.2 Secondary Endpoints

6.2.1 Secondary Safety Endpoints

- Incidence of individual PAE from the primary composite
- Incidence of Serious Adverse Device Effects (SADEs)
- Incidence of Serious Adverse Events (SAEs) within 7 days (early onset), 8-30 days (peri-procedural) and >30 days (late onset) of initial ablation procedure
- Incidence of non-serious adverse events
- Incidence of pre- and post-ablation asymptomatic and symptomatic cerebral emboli as determined by MRI evaluations
- Frequency, anatomic location, and size (diameter and volume) of cerebral emboli by MRI evaluations at baseline, post-ablation and during follow-up
- Incidence of new or worsening neurologic deficits post ablation and during follow up, compared to baseline.
- Summary of National Institutes of Health Stroke Scale (NIHSS) scores at baseline, post ablation and during follow-up.
- Summary of Montreal Cognitive Assessment (MoCA) scores at baseline, one-month follow-up and during further follow-up.
- Hospitalization for cardiovascular events (with hospitalization defined as prolonged stay ≥ 2 nights post index procedure or in-patient stay not concurrent with index procedure ≥ 1 calendar day)

6.2.2 Secondary Effectiveness Endpoints

- Percentage (%) of pulmonary vein isolation (PVI) touch-up by focal catheter among all targeted veins and by subject.
- Percentage (%) of subjects with use of focal catheter ablation for non-PV triggers
- 6-Month Documented Symptomatic AF Recurrence: Percentage (%) of subjects with freedom from documented, symptomatic atrial fibrillation (AF), atrial tachycardia (AT), or atypical (left side) atrial flutter (AFL) episodes (episodes >30 seconds on arrhythmia monitoring device from Day 91 to 180)
- 6-Month Documented AF Recurrence: Percentage (%) of subjects with freedom from documented, atrial fibrillation (AF), atrial tachycardia (AT), or atypical (left side) atrial

flutter (AFL) episodes (episodes >30 seconds on arrhythmia monitoring device from Day 91 to 180)

- 12-Month Documented Symptomatic AF Recurrence: Percentage (%) of subjects with freedom from documented, symptomatic atrial fibrillation (AF), atrial tachycardia (AT), or atypical (left side) atrial flutter (AFL) episodes (episodes >30 seconds on arrhythmia monitoring device from Day 91 to 365)
- 12-Month Documented AF Recurrence: Percentage (%) of subjects with freedom from documented, atrial fibrillation (AF), atrial tachycardia (AT), or atypical (left side) atrial flutter (AFL) episodes (episodes >30 seconds on arrhythmia monitoring device from Day 91 to 365)

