### 8.3 Post-Ablation Follow-up Schedule

The subject will be required to complete follow-up visits through 12 months post initial ablation procedure. Follow-up will be done at 7 days (phone call or clinic visit), 1, 3, 6 and 12 months (clinic visit).

Discharged subjects will receive a telephone call or have a clinic visit at 7 days (7D, day 6-8) post ablation procedure to assess any occurrence of Primary Adverse Events; otherwise, in-hospital surveillance will capture any Primary Adverse Events.

Follow-up visits should be scheduled according to the following timeframes: 1 month (1M, day 23-37), 3 month (3M, day 76-104), 6 month (6M, day 150 - 210) and 12 month (12M, day 315-405). Follow-up visit schedule should be based on the date of the index study ablation procedure and will not reset if subject undergoes a repeat AF ablation procedure.

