#### **At 1, 3, 6 and, 12month follow-up visits, the following assessments will be performed:**

- Adverse events (1M through 12M)
  - Cardiac and Anti-coagulation medication regimen (1M through 12M)
  - Atypical (left side) AFL/AT/AF recurrences and repeat ablations (1M through 12M)
  - NYHA Functional Class Scale (3M)
  - 12 Lead-ECG (if completed per standard of care)
  - Quality of Life questionnaire AFEQT (3, 6 and 12M)
  - Cardiac CT/MRA (3M): 3M follow-up CT/MRA should be performed for subjects presenting with symptoms on PV stenosis, using the same imaging technique as pre-ablation. Pre-ablation and post-ablation CT/MRAs of symptomatic subjects will be analyzed by a core lab to evaluate the level of PV stenosis.
  - Transtelephonic monitoring (TTM) (1M through 12M)  
Subjects will be provided with a TTM device at the 1M follow-up visit and asked to record and transmit a minimum of 1 transmission (60 seconds) every week through the end of month 5 of follow-up. Starting at month 6 of follow-up, subjects will be asked to record and transmit a minimum of 1 transmission (60 seconds) every month until the effectiveness evaluation period is completed (12 months post index procedure). Subjects will also be asked to transmit any symptom-triggered episode that occurs from the time they receive the TTM device through the 12M follow-up visit. A core lab will be used to evaluate and assess the TTM tracings.
- TTM monitoring will be conducted as follows:
- Distribution and start TTM monitoring by Month 1
  - <6M: Weekly transmission of at least 1 scheduled TTM recording
  - ≥6M: Monthly transmission of at least 1 scheduled TTM recording
  - Conduct and transmit TTM recording whenever symptoms are present
- 24 Hour Holter (6M and 12M)  
Holter monitor will be used at 6M and 12M follow-up visit to monitor the subjects' heart rhythm for 24 hours continuously. Following the 24h Holter, subjects will be

contacted by the site to verify if symptoms are experienced during 24h Holter. A core lab will be utilized to evaluate and assess the 24-hour Holter recordings.

For subjects in the NAE subgroup:

- Cerebral MRI, neurological exam and NIH Stroke Scale assessments will be performed at 1M, 3M, 6M and 12M visit in case observations were noted during previous assessments.
- MoCA and mRS assessments are mandatory at 1M visit. Subjects with findings of micro-emboli/neurologic deficits will undergo additional MoCA/mRS through 12M follow-up

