10. To be completed only if a previous mandated test was missed, or if subject reports neurologic difficulties between scheduled follow-up visits and unscheduled assessment per investigator approval.
11. Arrhythmia monitoring via TTM once per week as from 1M to the end of month 5 follow-up, once a month as from month 6 and whenever subject feels symptoms (day 30-365).
12. Arrhythmia monitoring via 24H Holter, site to contact subject and verify if any symptoms experienced during the Holter monitoring. Symptoms are to be reported in applicable CRF.

\* Within 60 days prior to procedure

\*\* A certified/qualified neurologist must perform neurologic exams at pre-and post-ablation and possibly at other follow-up visits, pending previous findings of micro-emboli/neurologic deficits.

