### 14.4 Interval Windows

Please refer to Table 8.7 A.

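### Do Holters allowed after day 180 and day 365 leave the rhythm endpoints undefined for compliant subjects?

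*SAP*

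**What the plan says.** SAP 6.2.2 defines two 6-month endpoints (day 91 to 180) and two 12-month endpoints, the latter as "episodes >30 seconds on arrhythmia monitoring device from Day 91 to 365". One endpoint of each pair is limited to symptomatic episodes; the other counts any documented episode.

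Protocol 8.3 sets the visit windows as "6 month (6M, day 150 - 210) and 12 month (12M, day 315-405" and ties the Holter to those visits: "Holter monitor will be used at 6M and 12M follow-up visit". Note 12 to Table 8.7-A adds, for the Holter, "site to contact subject and verify if any symptoms experienced during the Holter monitoring", so the Holter feeds the symptomatic endpoints too.

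Neither interval-window section sets a separate analysis window. Protocol 14.4 reads "Please refer to Table 8.7 A" and SAP 5 reads "Refer to protocol Table 8.7A".

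On TTM, Protocol 8.3 asks for at least one scheduled 60-second transmission a week through month 5 and one a month after that until 12 months after the index procedure. It also asks for transmission of any "symptom-triggered episode that occurs from the time they receive the TTM device through the 12M follow-up visit". Note 11 to Table 8.7-A has "once a month as from month 6 and whenever subject feels symptoms (day 30-365".

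SAP 11.5 makes all secondary analyses descriptive and leaves out subjects whose outcome is missing, without defining that for rhythm. SAP 11.5.2.1 reports a binary rate with an exact one-sided 95% lower bound. It also gives Kaplan-Meier estimates that censor event-free subjects with short follow-up at their last observation.

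**The concern.** The most sensitive scheduled rhythm test can lawfully take place after the endpoint it informs has closed. A subject seen late at 6M has no 6M Holter inside the 6-month period. One seen late at 12M may have only the 6M Holter inside the 12-month period. Both can be counted as free from recurrence, so less monitoring makes success more likely, chiefly for the two endpoints that include silent episodes.

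The plan does not say whether such a subject is evaluable in the binary analysis. If two analysts read the missing-outcome exclusion differently, they could publish different freedom rates from the same data. The two statements on the end of symptom-triggered TTM also disagree: it could run to the 12M visit, as late as day 405, or stop at day 365.

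**Working it through.** The plan states no figure on this point, so there is none to reproduce.

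**1. Window days after the cut-off** (Protocol 8.3 against SAP 6.2.2, days counted inclusively)

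| | 6M | 12M |
|---|---|---|
| Window length | 210 − 150 + 1 = 61 | 405 − 315 + 1 = 91 |
| Inside the period | 180 − 150 + 1 = 31 | 365 − 315 + 1 = 51 |
| After the cut-off | 210 − 180 = 30 | 405 − 365 = 40 |
| Share after | 30/61 = 49.2% | 40/91 = 44.0% |

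The windows are centred on day (150 + 210)/2 = 180 and day (315 + 405)/2 = 360, so a share near one half is built in. These are shares of days, not of subjects.

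**2. Does a late Holter leave the outcome unknown?** The endpoint is freedom from documented episodes on a monitoring device between two fixed days. It does not name the Holter or require a minimum amount of recording. A subject seen on day 200 or day 390 has been followed through the whole period. With no documented episode in it, the outcome is observed as free. An episode first seen later is not an event for that period. A 6M Holter on day 181 to 210 still falls within day 91 to 365 and counts for the 12-month endpoints.

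**3. What else monitors the period?** Scheduled TTM can show silent AF, but briefly. Day 91 to 180 is 90 days, and even a weekly transmission throughout gives at most about 90/7 ≈ 13 one-minute strips. A Holter gives 24 × 60 = 1,440 minutes, or 1,440/(1,440 + 13) ≈ 99% of the minimum scheduled recording time. TTM keeps the period monitored but does not replace the Holter. Symptom-triggered TTM also supports the symptomatic endpoints.

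**4. Who really has short follow-up?** It is the subject with an early 12M visit. A visit on day 315 to 364 (50 of the 91 window days) may end observation before day 365, by at most 365 − 315 = 50 days out of 365 − 91 + 1 = 275 (18%). The Kaplan-Meier analysis censors that subject, while the binary analysis has no written rule. The 12M visit and Holter were nonetheless completed as the protocol requires, so counting the subject as evaluable is the natural reading, and the Kaplan-Meier estimate beside it shows any difference. An early 6M visit causes no such loss, because follow-up continues.

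**5. What would an unsuitable missing-data rule do?** Assume 230 subjects, 184 event-free and 46 with recurrence. The lower bound is the 5th percentile of Beta(x, n − x + 1).

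| Rule | Late Holters (assumed) | Rate | Lower bound |
|---|---|---|---|
| Nobody excluded | any | 184/230 = 80.0% | 75.2% |
| Event-free late subjects dropped, failures kept | 10% | 166/212 = 78.3% | 73.1% |
| Same | 25% | 138/184 = 75.0% | 69.2% |
| Same | 44% | 103/149 = 69.1% | 62.3% |
| All late subjects dropped | 10% | 166/207 = 80.2% | 75.1% |

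The falls in rows two to four come from removing successes while keeping failures. They show why that exclusion would be wrong and do not estimate any bias in the plan as written.

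**6. The TTM end date.** A transmission on day 366 to 405 lies outside both periods, so neither version of the end date can change any of the four endpoints.

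**The case for a change.** The case for a change is that a choice affecting a published rate should be fixed before the data are seen. On the assumed figures above, one reading of the exclusion in SAP 11.5 gives 80.0% and another gives 75.0% at 25% late Holters. The Holter supplies nearly all the minimum scheduled recording time in the 6-month period, so TTM is a thin reply for silent AF. One sentence on evaluability, a count of late Holters and a supplementary analysis assigning each Holter to its nominal visit would use data already collected.

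Parts of this stand. The definition is absent, and early 12M visits have no binary rule. The recording-time comparison is fair, and the direction of any effect is towards overstating freedom from recurrence.

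It does not carry a change. The lower rates need an analyst to call a fully followed, event-free subject missing, which the endpoint's own wording does not support. Merely asking for a rule settles nothing, and offering missing as a neutral option invites the biased exclusion. Assigning Holters to nominal visits would leave the planned estimate as it is and add one whose follow-up length varies with visit date. Late Holters and their findings can be listed from the collected data without amending the plan.

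**Conclusion.** No change to the plan is needed. The mismatch between visit windows and endpoint days is real: 30 of 61 and 40 of 91 compliant days fall after the cut-offs. But the fixed-day definitions already say what counts, and a subject followed through the cut-off without an episode has an observed outcome, with or without a Holter inside the period. The unwritten parts, namely what makes a rhythm outcome missing and how an early 12M visit is treated in the binary analysis, are details that a competent analyst fills sensibly. The two TTM end dates are a clerical slip with no effect on these endpoints.

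This rests on analysts not excluding event-free late-Holter subjects while keeping failures. Some overstatement of freedom from recurrence remains possible, and its size cannot be derived from the documents. It would touch only secondary endpoints reported without hypothesis tests. The primary safety and effectiveness tests, the maximum of 230 subjects and the type I error do not depend on it.
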